Assessment	Screening	On-study treatment phase	End of Study	Follow up visits
Risk factor associated with GBS colonisation	x			

End of Study Definition

The main study will be deemed complete once all babies born to mothers in the study have reached six months of age.

The sub-study will be deemed complete when the last woman in the last maternity unit has delivered and her baby has reached 12 weeks of age. This will ensure that sufficient time has passed for any follow-up faecal samples to be received in the central microbiology laboratories at Bart's Health NHS Trust.

STATISTICAL CONSIDERATIONS

Test accuracy study

The sample size of the test accuracy study is dependent on the sensitivity of the rapid test. For the test to be proven useful we need to show that it will detect a higher proportion of GBS infections than other tests, but not at the cost of low specificity and/or unnecessary administration of IAP.

Results from GBS1 suggested that the most cost-effective test (if untargeted universal IAP was excluded) was antenatal culture for GBS at 35-37 weeks' gestation. In GBS1 the sensitivity of this test was 75.8% (95% CI 47.2% to 91.5%). Thus if we could prove that the sensitivity of rapid test was higher than 90% the results of the GBS2 study would be convincing. This is a stringent test — a lower threshold might also be adequate. We will not be comparing the rapid test with antenatal GBS culture testing within the study, but comparing with this result from external literature. Thus we will be undertaking a "one sample, sample size" computation comparing against a fixed value.

We have data from a systematic review on the performance of the new GBS test. From the meta-analysis of 9 studies, the pooled accuracy of the test was estimated, giving a sensitivity of 96.4% (90.8-98.6) and specificity of 98.9% (97.5-99.5). Sample size calculations are thus based on showing a test with sensitivity of 96.4% is greater than a fixed value of 90%. With a power of 90% to demonstrate this sensitivity, 167 cases of maternal GBS colonisation are required (or 136 at 80% power).

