A sample size of 676 would provide 90% chance of us accruing enough GBS colonised women to have 90% power to show the sensitivity of the GBS test to be statistically significantly (with p<0.05) greater than 90% should the meta-analytical estimate of its performance (96.4%) be correct whilst allowing for 10% loss from failed tests, based on the GBS prevalence observed in GBS1, which was 29.8% (89/299, 95% CI: 24.6%-35.2%). Of the 606 participants with data we would expect 167 to be GBS carriers and 439 to be negative for GBS colonisation. If the prevalence of GBS colonisation is actually at the lower 95% confidence interval from GBS1, namely 24.6%, then 673 total women will give 90% chance of observing 136 cases of GBS colonisation, including 10% lost tests.

The 95% Cis we would observe on sensitivities and specificities of 85%, 90%, 95% and 98% with a sample size of 676 (606 with data) are shown in **Table 1** and have adequate precision (sensitivity within 10%, specificity within 6%) for modelling.

Point estimate	CI for sensitivity (n = 167)	CI for specificity ($n = 439$)
85	78.7 – 90.1	81.3 – 88.2
90	84.2 – 94.0	86.8 – 92.7
95	90.9 – 97.9	92.5 – 96.8
98	94.8 – 99.6	96.2 – 99.1

Table 1: Confidence Intervals for sensitivity and specificity at various point estimates Cluster

randomised trial

The focus of this sample size calculation is on the effectiveness of the rapid GBS test within a cluster randomised trial (CRT) in which the number of clusters, in this case maternity units, is limited by the by the willingness of NHS Trusts to participate, but the number of potential participants is only limited by the duration of study period.

The CRT requires a minimum of 8 maternity units per screening strategy i.e. a total 16 units. Based on assumptions cited below, we estimate that the sample size per cluster will be approximately 83. This equates to a total sample size of approximately 664 participants per arm, and so therefore allows sufficient numbers of women to be recruited for the test accuracy study too.

As there are two arms (Standard Practice / Rapid Test), each of at least 664 participants this gives a projected sample size of 1,328 women. This has been rounded up to a target sample size of 1,340 women.

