For the sub-study looking at antibiotic resistance, of the 1,340 study sample size, we estimate that around 650 will be recruited from centres in London and the South-East. Of these, 325 will be assigned to the rapid test arm. Assuming that one out of five women decline their invitation to participate in the sub study, we estimate that the total sample size will be around 260 participants.

The proportion of women receiving IAP for prevention of GBS transmission under a risk factor based strategy is expected to be in the region of 50% to 75%. In GBS1, only 47% of women with risk factors received IAP. We expect that greater understanding and implementation of the RCOG and NICE guidelines will have improved this figure in contemporary practice, but it is unlikely that there will be perfect compliance with RCOG/ NICE guidelines. We thus estimate an IAP rate of 75% to be reasonable. This primary outcome is a process outcome and so the within-cluster correlation of this outcome (the ICC) is expected to be higher than it would be for a clinical outcome. We have therefore considered the sensitivity of our

calculations to a range of proportions in the risk factor-based screening strategy group and a range of ICC values which we believe to be quite conservative. All of our calculations allow for 90% power and 5% significance.

Guided by the need to have at least 676 women to fulfil the needs of the test accuracy study, and under a range of values for the risk-factor based strategy IAP rates and values of ICC, we have worked out the difference detectable and equivalent relative risk reduction (RRR), shown in **Table 2**.

IAP rate in risk- factor screening strategy	ICC=0.2	ICC = 0.1	ICC = 0.05	ICC = 0.01
75	38% (RR = 0.51)	48% (RR = 0.64)	55% (RR = 0.73)	63% (RR = 0.84)
60	22% (RR = 0.37)	32% (RR = 0.53)	39% (RR = 0.65)	47% (RR = 0.78)

Table 2: Range of relative risk reductions achieved with a range of important parameters

The CRT would have around 90% power to detect a reduction in the proportion of women prescribed antibiotics from 75% to 63% (RRR of about 20%) for a low value of the ICC; to a reduction from 75% to 38% for a very conservative value of the ICC (0.2), equating to a relative risk reduction of 50%.

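### The protocol calls about 664 women per arm sufficient for the accuracy study although its own requirement is 676, and it misstates the expected carriers and one relative risk reduction

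*Protocol*

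**What the plan says.** All references are to the protocol, under Statistical Considerations unless noted.

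- **Test accuracy study, hypothesis.** "Sample size calculations are thus based on showing a test with sensitivity of 96.4% is greater than a fixed value of 90" per cent. "With a power of 90% to demonstrate this sensitivity, 167 cases of maternal GBS colonisation are required (or 136 at 80% power").
- **Test accuracy study, total.** "A sample size of 676 would provide 90% chance of us accruing enough GBS colonised women to have 90% power" for showing sensitivity "statistically significantly (with p<0.05) greater than 90" per cent. The inputs are a prevalence of 29.8% (89/299) and a 10% loss from failed tests. A second scenario takes 24.6% prevalence, 136 cases and 673 women.
- **Test accuracy study, expected counts.** "Of the 606 participants with data we would expect 167 to be GBS carriers and 439 to be negative for GBS colonisation".
- **Cluster randomised trial, size.** At least 8 units per arm with about 83 women each: "This equates to a total sample size of approximately 664 participants per arm, and so therefore allows sufficient numbers of women to be recruited". That sentence refers to the accuracy study. Two arms give 1,328, rounded up to 1,340.
- **Cluster randomised trial, detectable effect.** "Guided by the need to have at least 676 women to fulfil the needs of the test accuracy study", Table 2 lists detectable rates. The text then describes a reduction "from 75% to 63% (RRR of about 20%) for a low value of the ICC". Table 2 prints RR = 0.84 for that cell.
- **Who is swabbed.** Specimen identification, processing and storage, and Lab Procedures, place the maternal swabs for the rapid test and the reference culture in rapid-test units. Under Obtaining a vaginal-rectal swab, the packs in the other units hold data forms only.

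**The concern.** The accuracy study can draw only on the rapid-test arm. That arm is planned at 664, or 670 if the rounded target is split equally. Neither reaches 676, yet the text says the number suffices and, a few paragraphs later, again treats 676 as the minimum. No stated target meets it.

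Two nearby figures do not follow from the inputs printed beside them: the expected number of carriers and the relative risk reduction at the low ICC.

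What is at stake is the stated 90% assurance of reaching 167 carriers and the accuracy of figures that are likely to be carried into reports.

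**Working it through.** **1. Reproduce the required carriers.** One-sample test of a proportion, normal approximation, p0 = 0.90, p1 = 0.964, two-sided 5%:

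n = [(z_α√(p0(1−p0)) + z_β√(p1(1−p1))) / (p1−p0)]²

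- 90% power: [(1.96 × 0.300 + 1.282 × 0.186) / 0.064]² = 166.9, so 167.
- 80% power: [(1.96 × 0.300 + 0.842 × 0.186) / 0.064]² = 135.4, so 136.

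Both match the protocol. A one-sided 5% test would give 131 and 104, so the plan used two-sided 5%.

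**2. Reproduce the total.** The smallest n with a binomial probability of at least 0.90 of 167 or more carriers at 29.8% is 608; 608/0.9 = 675.6, so 676. For 136 cases at 24.6% it is 606; 606/0.9 = 673.3, printed as 673. Both match.

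**3. Size of the rapid-test arm.** 8 × 83 = 664, which is 12 short of 676 (1.8%). 1,340/2 = 670, which is 6 short (0.9%).

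**4. What those sizes deliver after the 10% loss.**

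| Women | With data | P(≥167) at 29.8% | P(≥136) at 24.6% | Average exact power at 29.8% |
|---|---|---|---|---|
| 664 | 598 | 85.2% | 86.5% | 91.0% |
| 670 | 603 | 88.0% | 88.8% | 91.2% |
| 676 | 608 | 90.4% | 90.8% | 91.5% |

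The last column is the power of the exact binomial test of sensitivity (upper tail 0.025), averaged over the random number of carriers. If the 10% loss is treated as random rather than fixed, P(≥167) is 84.5%, 87.6% and 90.1%. At 24.6% prevalence the average power is 83.4%, 83.8% and 84.2%.

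**5. Expected counts.** 606 × 0.298 = 180.6, about 181 carriers, leaving 425 negatives. The printed 167 and 439 would need a prevalence of 167/606 = 27.6%. So 167 is the required count, reached with about 90% probability, and not the expectation. Also, 676 × 0.9 = 608; the 606 belongs to the 673-woman scenario.

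**6. Relative risk reduction.** 1 − 63/75 = 0.16, which agrees with Table 2 (RR = 0.84). A 20% reduction from 75% would end at 60%. The companion figure is fair: 1 − 38/75 = 49%, printed as 50%.

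**7. The detectable rates.** At ICC 0.01 the design effect is 1 + 82 × 0.01 = 1.82. With 8 units of 83 per arm, power for 75% against 63% is about 91% using a t reference with 14 degrees of freedom. Across the cells of Table 2, power on that basis is 90–93%, so the rates themselves stand.

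**The case against.** **The sizes are floors.** The protocol hedges its arm size as approximate and asks for a minimum of 8 units. It says numbers are limited only by the length of the study period. Accrual and study initiation roll-out gives an average of 71 eligible deliveries per site per four weeks and a 4–5 week period. Five weeks would give 71 × 5/4 = 88.75 per unit, or 710 per arm. The need for 84.5 per unit (676/8) is met at about 4.8 weeks. This stands: the shortfall lies in the stated targets and is easily closed. It does not rescue the statement that 664 is sufficient.

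**The power loss is negligible.** This also stands. Missing 167 by a few carriers barely changes power, and the average falls only from 91.5% to 91.0%. A reader might infer an underpowered accuracy study; the protocol's inputs do not support that.

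**Further losses.** A reader might add women who decline the swab or have no culture result, and conclude that the chance of 167 carriers collapses. The protocol gives no rate for such losses. It treats 10% as the most it expects for failed tests (Antibiotic administration), excludes women likely to deliver imminently, and keeps spare swabs on the ward. Any such figure would rest on an assumed rate and does not belong in this point.

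**Expected carriers.** Using 167 makes the sensitivity intervals in Table 1 slightly conservative. With 181 and 425 the limits move by at most half a percentage point. No design decision changes.

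**Detectable effect.** A reader might say that the minimum detectable effect is misstated. It is not: 75% to 63% is correct and Table 2 has the right RR. Only the bracketed percentage is wrong, and it is hedged. The caption of Table 2 speaks of relative risk reductions while the cells show rates and RRs, but each cell is labelled, so that is cosmetic.

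**Conclusion.** Three statements are wrong as written.

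1. 664 women are called sufficient, and 670 is the most the target implies, against a requirement of 676. The assurance of 167 carriers is about 85–88%, not 90%.
2. The carriers and negatives called expected (167 and 439) are built on the required count. The expectation is about 181 and 425.
3. The relative risk reduction for 75% to 63% is 16%, not about 20%.

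The practical effect is small. Average power for sensitivity remains about 91%, and the sample-size derivations (167, 136, 676, 673) and the detectable rates in Table 2 reproduce. The result assumes an equal split of the 1,340, the protocol's 29.8% prevalence and its 10% loss. At 24.6% prevalence the chance of 136 cases is 86.5–88.8%, against the stated 90%.

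**What to change.** - **Sufficiency statement.** Replace it with the chance that the planned arm delivers: about 85% at 664 and 88% at 670. Then reconcile it with the later minimum of 676. If 676 is to be kept, plan about 85 women per unit: 8 × 85 = 680 per arm, 1,360 in total. At 71 per four weeks that takes 85/17.75 = 4.8 weeks, inside the stated window.
- **Carriers.** State 167 as the number required and about 181 as the number expected, with about 425 negatives of 606. For 676 women, give 608 with data.
- **Relative risk reduction.** Change about 20% to 16%.

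Cost: a few sentences. Restating needs no extra recruitment, and the assurance becomes slightly less favourable. Keeping 676 by way of 85 per unit adds 20 women to the 1,340 target.

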By linking the number on the pot with that of the mother the profile of any GBS, MRSA, VRE, and ESβL obtained from the mother's vaginal - rectal sample will be compared with that of any GBS, MRSA, VRE, and ESβL obtained from the baby's faecal sample at around six weeks old. Once the last faecal sample has been processed the local midwifery staff will be supplied with a list of trial numbers of those mothers who returned samples of their child's faecal material and asked to supply data on the mode of delivery the woman experienced alongside any maternal co-morbidities. These data will be combined to see if there is any correlation between the colonising species and the mode of delivery, and / or maternal co-morbidities.

[figure not shown]
The data flow for the relatedness sub-study is shown in Figure 5 on the next two pages.

Figure 5: The data flow for the relatedness sub-study

GBS2: Data flow pathway—Swab 3

[figure not shown]

Version 1.0 22nd December 2015 GBS2 Page 27 of 81

GBS2: Data flow pathway—Swab 3

[figure not shown]

The study schema in centres assigned a rapid test in 1) The West Midlands [Figure 6], and 2) London and the South-East [Figure 7], followed by 3) those centres without a rapid test [Figure 8] are shown below:

Study Schema

Figure 6: Centres in the West Midlands assigned a rapid test

[figure not shown]

Figure 7: Centres in London and the South-East assigned a rapid test

Centres who are NOT assigned a rapid test Woman presents to labour ward woman have GBS risk factor emerged? Give antibiotics Are antibiotics linically indicated? N Has the woman requested Antibiotics 2 N Don't give antibiotic Monitor Are antibiotics clinically indicated?

Figure 8: Example pathway in centres not assigned a rapid test

Current rates of intrapartum prophylaxis in participating maternity units

Information will be sought from all participating units regarding their current rate of administration of IAP for GBS transmission. This can be derived from audit, interrogation of hospital records or pharmacy prescribing databases.

Randomisation of maternity units

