The purpose of the obtaining the baseline current IAP usage rates is to stratify the randomisation of clusters. With a relatively small number of clusters it may be inappropriate to attempt to pair clusters. As clusters will be randomised in up to four waves, it is more appropriate to stratify the randomisation of clusters within each wave by baseline IAP rate. Maternity units will be randomised to follow either the risk factor based screening strategy or the rapid test strategy to direct the decision to offer IAP.

Version 1.0 22nd December 2015 GBS2 Page 31 of 81

Risk based screening units (i.e. those not assigned a rapid test system)

All women considered eligible for the study according to the risk factors for GBS transmission described should be offered IAP.

If a woman is pyrexic, or suspected or confirmed to have chorioamniotis, broad spectrum antibiotics (e.g. fourth generation cephalosporins) should be given immediately.

The use of IAP will be collected, including information of whether IAP was declined or deemed too late given the progression of the labour, along with the date and time the IAP was initiated.

Rapid test screening units

Supply of trial consumables

Units randomised to receive the rapid point of care test will be supplied with a Cepheid GeneXpert GBS rapid testing system plus a sufficient number of GeneXpert GBS test cartridges and other consumables to cover the number of women projected to have GBS risk factors presenting to their unit during the study period. Should stocks of consumables or test cartridges start to run low (to a level of around 25% of that initially supplied) then the centre should contact the Trials Office in Birmingham who will arrange re-supply.

Obtaining a vaginal-rectal swab

The use of the rapid test for screening will be restricted to women who present to the labour ward and who exhibit at least one of the risk factors associated with GBS colonisation.

Depending on the stage of labour the swabs will be obtained by either the woman herself, or a suitably qualified, trained, and locally approved member of the woman's care team. This could be on admission to the labour ward, before a vaginal examination is performed, or after a risk factor is detected - for example, maternal fever is observed.

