We have not acknowledged varying cluster sizes in our calculations, as we consider the coefficient of variation of unit delivery sizes to be small (approximately 0.21 based on annual delivery rates for 2013) and can be altered by varying the study duration at maternity units. Given our conservative assumptions, and that the impact of the rapid test on the rate of IAP provided is expected to be large, it is expected that the impact of any varying cluster sizes will be minimal.

Analysis methods

Test accuracy study

The accuracy of the rapid test for detection of GBS colonisation will be expressed as sensitivity, specificity, positive and negative predictive values, and positive and negative likelihood ratios, along with their associated 95% confidence intervals.

Cluster randomised trial

The baseline characteristics, for example parity, ethnicity, risk factors and gestational age at onset of labour will be summarised as means and standard deviations, or medians and inter-quartile ranges, grouped by unit allocation (risk factor based screening or rapid test based screening).

Analyses of outcomes will be by intention to treat. As randomisation will be at the maternity unit level, appropriate statistical methods to account for the clustering within units will be used in the analysis.

The primary aim of the study is to evaluate whether the proportion of women prescribed IAP for prevention of GBS transmission differs between the screening strategy groups. In statistical terms the null-hypothesis, that of no difference can be tested using a mixed logistic regression model with prescription of IAP as the dependent variable, study screening strategy group as the independent variable, and maternity unit as a grouping (random effect) variable. These models will be fitted using population averaged models (similar to multilevel models) using GEE methods in STATA. Population averaged models, as opposed to random effects models, will be used as within the framework of cluster randomised trials: random effects models both lack appropriate interpretation and might be biased.[52] Similar models will be fitted for secondary outcomes and appropriate link functions used for outcomes which are not binary.

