Primary analysis will be unadjusted, but secondary analyses will adjust for prespecified and clinically important baseline covariates. These will include gestational age, and presence of individual risk factors, and maternity unit level covariates such as size. We will allow for clustering at the maternity unit level. The primary analysis will be a complete case analysis. However, missing data will be reported and associations between outcomes explored. Depending on the nature of these associations and the extent of the missing data, sensitivity will be explored by means of multiple-imputation.

The primary outcome will be considered significant at the 5% level (and so the 95% Cis reported); whereas other secondary outcomes will be interpreted cautiously as the CRT is not necessarily powered to detect a difference in these. Reports of interim analysis will be supplied in confidence to the DMEC during the recruitment period. Final analysis will be performed once all babies born to mothers in the study have reached six months of age.

Relatedness sub-study

The proportions of mothers and infants carrying antibiotic resistant bacteria will be documented and the degree to which the strains are indistinguishable when characterised using techniques which include; matrix-assisted laser desorption ionization—time of flight mass spectrometry, antibiotic susceptibility profile, and genetic analyses (including analysis of resistance mechanisms) will be documented. These data will allow an estimate of the extent to which mothers and infants at around six weeks of post-natal life carry indistinguishable strains of resistant bacteria. This data will be used to inform the design of more detailed studies aimed at better understanding transmission pathways with the objective of defining potential interventions.

Accrual and study initiation roll-out

We will not attempt to start recruitment in all sites simultaneously but instead plan on opening equal numbers of control and experimental sites in staggered waves. The burden of supporting sites will be spread over 12 months and lessons learnt in the first wave will be carried forward to the management later units.

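### Units are randomised in strata of baseline IAP rate, but the primary analysis is fixed as unadjusted, which forgoes precision if that rate predicts the outcome

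*Protocol*

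**What the plan says.** Under Methodology, the protocol asks every unit for its current IAP rate: "Information will be sought from all participating units regarding their current rate of administration of IAP for GBS transmission". Under Randomisation of maternity units it gives the reason: "The purpose of the obtaining the baseline current IAP usage rates is to stratify the randomisation of clusters". Clusters enter in up to four waves, and the protocol concludes that "it is more appropriate to stratify the randomisation of clusters within each wave by baseline IAP rate".

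Under Statistical considerations, Analysis methods (Cluster randomised trial), the primary model has prescription of IAP as the outcome, with "study screening strategy group as the independent variable, and maternity unit as a grouping (random effect) variable", fitted by GEE. Adjustment is then settled: "Primary analysis will be unadjusted, but secondary analyses will adjust for prespecified and clinically important baseline covariates". On the secondary covariates it adds: "These will include gestational age, and presence of individual risk factors, and maternity unit level covariates such as size".

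So the stratifier has a stated role in allocation and none in any analysis, and no reason is given. The primary model is a closed statement. The secondary list is open, so baseline IAP rate is unnamed there but not ruled out.

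**The concern.** Stratifying on a predictor of the outcome makes the arms more alike than chance would, so the true sampling variance of the arm difference falls. An analysis that leaves the stratifier out still counts the between-unit variation due to it in its standard error. The reported standard error is then larger than the true one: intervals are too wide and the test runs below its nominal 5%.

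Adjustment also removes predictable between-unit variation that stratification only balances. That matters here because between-unit variation is what limits a trial of 16 units. At a control rate of 75%, Table 2's detectable difference grows from 12 points (75% to 63%, ICC 0.01) to 37 points (75% to 38%, ICC 0.2). The covariate must be known before a unit can be allocated, so using it needs no new data.

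**Working it through.** **Inputs from the protocol.** 8 units per arm, 16 in total; about 83 women per unit; control IAP rate 75%; 90% power; 5% significance, taken as two-sided; ICC 0.2, 0.1, 0.05 and 0.01; up to four waves, stratified by baseline IAP rate.

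**Assumed.** The correlation between a unit's baseline rate and its trial-period rate. The protocol does not give it, so 0 to 0.7 is shown.

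**1. Table 2 reproduced.** Effective number per arm = 8 × 83 / (1 + 82 × ICC), which is 664/17.4 = 38.2, 664/9.2 = 72.2, 664/5.1 = 130.2 and 664/1.82 = 364.8 for ICC 0.2, 0.1, 0.05 and 0.01. Solve

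p1 − p2 = (t₀.₉₇₅ + t₀.₉₀) × √[(p1(1−p1) + p2(1−p2))/n_eff]

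with 14 df, where the multiplier is 2.145 + 1.345 = 3.490. For p1 = 75% this gives p2 = 38.2, 47.8, 54.8 and 63.2%, against 38, 48, 55 and 63% in the table. The planned power therefore takes no credit for stratification or adjustment.

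**2. Simulation at those differences.** 20,000 trials per setting; four waves of four units; two baseline strata per wave, allocated 1:1 within stratum; beta-distributed unit rates; 83 women per unit. The unadjusted cluster-level t test (14 df) is compared with cluster-level analysis of covariance on baseline rate (13 df). Power is shown unadjusted → adjusted, in %.

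| Correlation | ICC 0.2 (75 v 38) | ICC 0.1 (75 v 48) | ICC 0.05 (75 v 55) | Change in points |
|---|---|---|---|---|
| 0 | 87.4 → 86.2 | 88.0 → 86.6 | 89.0 → 87.6 | −1.2 to −1.4 |
| 0.3 | 87.8 → 89.0 | 88.5 → 89.3 | 89.4 → 89.8 | +0.4 to +1.2 |
| 0.5 | 88.5 → 93.2 | 89.3 → 93.6 | 89.7 → 93.6 | +3.9 to +4.7 |
| 0.7 | 89.7 → 98.4 | 90.3 → 98.3 | 90.9 → 98.0 | +7.1 to +8.7 |

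A separate simulation of the same comparison gave about −1.5, +4 to 5 and +6 to 8 points at correlations 0, 0.5 and 0.7. The conclusion uses these slightly more cautious figures.

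**3. Type I error at the same three ICCs.** Unadjusted: 3.7 to 3.9% at correlation 0.5 and 2.4 to 2.8% at 0.7. Adjusted: 4.8 to 5.3% throughout. The cause shows at ICC 0.1, correlation 0.7, with no true difference. The mean reported unadjusted standard error is 0.0714 against a true 0.0625, and 0.0714/0.0625 = 1.14, so it is 14% too large and the 95% interval covers 97.6%. Adjusted, the figures are 0.0543 and 0.0552, with 95.2% coverage.

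**4. Baseline predictive in control units only.** Under Antibiotic administration, rapid-test units are asked to offer IAP on the test result or at the woman's request, so previous practice may predict little there. With correlation 0.7 in control units and 0 in test units, power moves 88.1 → 89.6, 88.7 → 90.4 and 89.3 → 90.4% at ICC 0.2, 0.1 and 0.05, a gain of 1.1 to 1.7 points. With 0.5 in control units only, the change is −0.3 to +0.4.

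**5. Dependence on the test used.** With an uncorrected robust standard error and normal quantiles, as an uncorrected GEE would use, the unadjusted type I error is 8.8% at correlation 0 (ICC 0.1 and 0.05). At ICC 0.05 to 0.2 it is 6.8 to 7.2% at correlation 0.5 and 4.9 to 5.3% at 0.7. The over-wide intervals in step 3 belong to a test already valid for 16 clusters.

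**The case against.** The strongest reply is that nothing promised is lost. Table 2 is built without adjustment, and the unadjusted test keeps 87 to 91% power at its 75% row. That stands: the loss is a gain not taken.

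Second, the gain rests on a correlation that the protocol does not give, and the intervention replaces the practice that baseline measures. That also stands, and step 4 shows how far the benefit can shrink. Baseline rates may come from audit, hospital records or pharmacy databases, so the measure may be noisy and differ between units, which would lower the correlation further. Against this, the protocol itself treats the rate as informative enough to govern allocation.

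Third, the simulations use cluster-level tests and not the planned GEE. This limits the precision of the figures, not their direction.

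A reader might infer more than the documents support:

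- **That power is only about 69%, against 88% with adjustment.** Such figures arise for 75% v 55% at ICC 0.1 with half the between-unit variance explained. Table 2 pairs 55% with ICC 0.05; at ICC 0.1 its detectable rate is 48%. The protocol never claims 90% power for that combination.
- **That the error bars are wrong in a dangerous direction.** With a valid small-sample test they are too wide. This omission neither biases the estimate nor inflates false positives. The inflation in step 5 comes from a missing small-sample correction, which is a separate matter.
- **That the secondary analyses leave the stratifier out.** The list is open-ended, so it may yet be included.

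**Conclusion.** The point holds as a worthwhile, nearly free improvement to a stated choice, not as an error that undermines the trial. If baseline IAP rate predicts trial-period IAP in both arms, an unadjusted analysis with a valid small-sample test has type I error of about 2.5 to 4% at correlations of 0.7 to 0.5, and its intervals are correspondingly too wide. At Table 2's detectable differences for ICC 0.05 to 0.2, adjustment is worth about +4 to 5 points of power at correlation 0.5 and +6 to 8 at 0.7 (close to 9 in one setting of the table above). It is worth 1 to 2 points if prediction is confined to control units at 0.7, and it costs about 1.5 points if there is none. All of this rests on assumed correlations and on cluster-level tests standing in for the GEE.

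**What to change.** State the primary GEE model as strategy group plus unit baseline IAP rate, entered as one continuous unit-level covariate or as the stratum used for randomisation. Name the small-sample correction and take one degree of freedom fewer (13 instead of 14 with 16 units); a stratum factor with more than two levels would take more. Keep the unadjusted estimate as a sensitivity analysis. Specify this before outcome data are seen, since adding the covariate afterwards would be a post hoc choice.

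Wave is also part of the stratification and is named in no analysis. Four waves would take three further degrees of freedom (13 − 3 = 10), so wave is better left to a sensitivity analysis.

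The cost is one line of model specification, one degree of freedom, no new data, and about 1 to 2 points of power if baseline proves uninformative.
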